# 9.3 Confidentiality

All data and records generated during this study will be kept confidential in accordance with Institutional policies and HIPAA on subject privacy. The Investigator and other site personnel will not use such data and records for any purpose other than conducting the study. Hard data will be kept in locked file cabinets in the CAPP suite, and will be destroyed 10 years after the end of the study unless subjects consent to contact regarding future research. Any soft data or electronic data will be password protected and kept on a secure CHOP computer.

# 9.4 Regulatory and Ethical Considerations

### 9.4.1 Data and Safety Monitoring Plan

The study sponsor will appoint members to a Data and Safety Monitoring Board. Reporting on study conduct, safety measures, data collection and analysis will be provided to the DSMB

#### 9.4.2 Risk Assessment

Potential risks directly related to the study are minimal. Children may have difficulty with pulmonary function testing, which may be included as a part of their usual care depending on the child's healthcare team, or collected by a trained CHW. Risks indirectly related to the study, particularly in a group of children where no evidence-based interventions are being conducted may include challenges with asthma management which may lead to ED visits or hospitalizations.

Another risk is the potential breach of confidentiality for participant data. When possible, data will be coded by study personnel through the use of participant identification numbers. Any screening referrals from the community will be faxed to a confidential fax line. In addition, participants could potentially feel discomfort with engaging in any of interventions, as questions may be posed requiring personal information.

### 9.4.3 Potential Benefits of Trial Participation

Direct benefits: Community Health Workers providing the connection between the home, school and primary care practice may reduce the burden on caregivers and facilitate asthma management for school-aged children. Additionally, as community residents, CHWs are knowledgeable about the public school system and can help parents connect to local resources. Participants will also benefit from asthma management education.

Indirect benefits: This project utilizes a pragmatic, integrated and sustainable design with evidence-based interventions to reduce asthma disparities in poor, minority children. We have engaged stakeholders with experience in the community, school district, health plans and health care systems to implement community and evidence-based interventions. These interventions, if proven successful, will reduce the disproportionate impact of asthma on minority children through the number of missed school days, ED visits and hospitalizations due to asthma exacerbations and also create a sustainable care-coordination model that can be replicated in other communities.

#### 9.4.4 Risk-Benefit Assessment

There are minimal risks due to the possibility of loss of confidentiality and possible discomfort from answering questions. There are significant benefits to be gained through participation in the primary care CHW program. We will, to the best of our capabilities, ensure minimal risks by 1) assigning study identification numbers to patient records and for data collection purposes. Only these numbers will be shared with third parties. 2) The caregiver will always have the option of refusing to answer or participate in any component of the study without change to usual care.

## 9.5 Recruitment Strategy

We will screen electronic health records to recruit 640 parent-child dyads with children ages 5-13 years old with uncontrolled asthma (evidenced by one or more asthma exacerbations requiring oral steroids -OR- one hospitalization within the past year -OR- two ED visits within the past year) from up to five primary care centers (CHOP CN – Cobbs Creek, CHOP CN - Karabots, CHOP CN - South Philadelphia, The Pediatric and Adolescent Medicine Centers of Philadelphia (PAMCOP) and Federally Qualified Health Centers) who serve families who live in the seven West Philadelphia ZIP codes (19104, 19131, 19139, 19142, 19143, 19151, 19153). In addition, CHOP Emergency Department (ED) will screen electronic health records and refer children for enrollment at the primary care sites when they are seen in the ED. The majority of eligible participants will be identified through medical record review and documented on the screening form completed by the CHW or research assistant in the primary care centers or CHOP ED. A waiver of consent will be used to facilitate this process. If additional information is needed to determine eligibility, the CHW will approach families to see if they are interested in being screened for any missing information on the screening form. The screening form will be reviewed by study staff (SC and PI) to confirm study eligibility.

We will also post flyers in our CHOP primary care centers, CHOP ED, and also in partnering community centers. These flyers will contain the CAPP main phone number and email address for families interested in participating in the study. Community partners can also refer children at community events for study screening by research staff.

The Recruitment Enhancement Core (REC) at CHOP provides assistance with recruitment plan development and may assist us in identifying and contacting potential participants using the Clinical Reporting Unit (CRU), the CHOP Recruitment Registry, social media and internal communication resources. The REC also engages community partners and facilitates outreach on behalf of the research Institute and CHOP research studies.

#### 9.6 Informed Consent/Assent and HIPAA Authorization

For the screening process, a waiver of consent documentation and HIPAA will be used. For children and parents/caregivers interested in the study, they will be given explicit information regarding the purpose and procedures of the program, the family will then be asked if they have any questions. The family will be given a consent form that will be read to them by a member of the study team describing the study procedures, the purpose of the study, that their consent to participate in the study is strictly voluntary, and that should they consent, they have the right to end study procedures at any time. Parents who agree to participate will sign an IRB-approved combined informed consent form and HIPAA authorization on paper using a handwritten signature or on a tablet device using an electronic signature. Consent discussions may be held remotely by phone or through videoconference using a HIPAA-compliant application licensed by CHOP including but not limited to BlueJeans and Skype. For consent discussions held remotely, through video conferencing or by telephone, parents will be provided with a REDCap survey link to the informed consent and HIPAA authorization to review and sign electronically. Alternatively, parents with limited internet access can provide verbal consent for participation. Electronic informed consent forms will be stored and managed in the study's REDCap database. Child

assent will be handled in the same fashion. All participants will receive a copy of the signed informed consent form and HIPAA authorization. The electronic consent form will include the patient and caregiver's typed names and written signatures using a stylus pen. Participants who provide an electronic signature will receive a copy of the signed document by email or a printed copy will be provided at the conclusion of the consent meeting. Participants providing verbal consent will receive a copy of the informed consent and HIPAA authorization and documentation of verbal consent via U.S. postal mail.

# 9.7 Payment to Subjects/Families

### 9.7.1 Payments to subject for time, effort and inconvenience (i.e. compensation)

Data will be collected for all individually randomized participants at baseline, 3, 6, 9 and 12 months by the research assistant or primary care CHW in person or by phone. Participants will be compensated \$25 for each visit with data collection at baseline, 3, 6, and 9 months and \$45 for the end of study visit at 12 months.

#### 9.7.2 Gifts

During the study, birthday and holiday cards will be sent by mail to enrolled participants. Annually, a small holiday gift such as a jump rope, sports ball or a similar item valued at no more than \$10 may be provided to each enrolled child.

### 10 PUBLICATION

Data may be used for scientific papers and presentations at medical conferences. All data is reported in aggregate form and individuals are never identified.

### **APPENDIX**

- A. Initial Home Environmental Assessment
- B. Follow-up Home Environmental Assessment
- C. Initial School Environmental Assessment
- D. Follow-up School Environmental Assessment
- E. Care Coordination Goals Form/Tracking Sheet
- F. Asthma Control Tool
- G. Asthma Knowledge Quiz (Pre/Post)
- H. Caregiver Needs Assessment survey
- I Caregiver Satisfaction Survey
- J. MDI checklist
- K. Paediatric Asthma Caregiver's Quality of Life Questionnaire (PACQLQ)
- L. Pulmonary function test data collection form
- M. Intake Survey
- N. 3, 6, 9, 12 Month Follow-up Survey
- O. CARAT Survey
- P. You Can Control Asthma Curriculum

Study Title:	West Philadelphia Asthma Care Implementation Plan (WEPACC)
Short Title:	West Philadelphia Controls Asthma
Document:	Statistical Analysis Plan
Document Date:	September 13, 2022
Regulatory Sponsor:	NHLBI
eIRB Number:	17-013892
NCT Number:	NCT03514485
Authors:	[name] [name] [name]

Funding Sponsor

NHLBI National Heart, Lung, and Blood Institute [name] United States

Principal Investigator

[name] Children's Hospital of Philadelphia [name] [contact] email: [contact]

[name] Division of Biostatistics Department of Biostatistics, Epidemiology, and Informatics Perelman School of Medicine University of Pennsylvania email: [contact] This statistical analysis plan (SAP) governs the analysis of the WEPACC factorial cluster randomized controlled WEPACC study. This SAP attempts to cover all points outlined in the CONSORT guidelines for reporting cluster randomized trials. (See Appendix) (Campbell 2010).

This SAP will be updated regularly but will be finalized formally before any analysis of outcomes.

Date of Finalization of SAP: September 13, 2022

1. Questions of interest

Stated formally, the primary question of interest is as follows. If a group of children were alternatively assigned to the following exposure groups (a= attended a school at which the specified intervention was in place AND was exposed to the specified child-level intervention, b=attended an intervention school but did not have access to the child-level intervention, c=did not attend an intervention school put received no child-level intervention, and d=did not attend an intervention school and received only usual care, then are there important differences in outcomes across the four groups?

All outcomes for the primary analysis will be measured at the child level, but in some cases (see below) will be aggregated to the school level.

2 Design

The overall design will stratify participating schools into at least 5 groups to enhance balance at baseline in school characteristics (size, location, charter status). Randomization of schools to the school-level intervention (S⁺) or usual practice (S⁻) will be stratified by these predefined groups. At the time asthma patients present in the clinics and consent to participating, these patients will be randomized to navigator assistance (child-level intervention) (A⁺) or usual care (A-), and that randomization will be stratified by school and clinic of recruitment. Allocation concealment will be preserved by randomly permuted block, and this approach will also preserve balance of intervention arms within schools over time. This randomization plan will produce a 2by-2 factorial design, partly clustered (by school). (Table 1) Schools and children are followed over time.

Table1	Child-level		level
		intervention	
		A+	A-
School	S+	a	b
Level	S-	c	d
	none	e	f

The proposed design results in 6 groups of children. The cells a,b,c,d will permit comparison of any of the 3 combinations of school and child intervention (a,b,c) against the group that has neither(d). At the same time, it will permit marginal analysis of the effect of the school intervention (a+b vs c+d), and the marginal effect of the navigator intervention (a+c+e vs b+d+f). For each of the cells of interest, we collect baseline data on

children and then follow schools and children over time. This design avoids contamination and interference through cluster randomization but benefits from added power of a longitudinal analysis. The factorial layout permits estimation (and testing) of interaction between the school and

individual interventions. It also allows for use of data from children who are from nonparticipating schools.

3 Randomization

3.1 Randomization of Schools

Schools were randomized in several waves to meet the evolving requirements of the study design.

Randomization Wave 1

For the cluster randomization of the 22 schools, we adopted the following approach. First, because two of the 22 schools were charter schools, we immediately paired them and randomly assigned one of the pair to the intervention and the other to control.

Second, for the remaining 20 schools we implemented covariate constrained randomization to achieve balance on the three key covariates: enrollment size, facility index (%), and percent with attendance>- 95% of the time. These 3 covariates are all continuous. For that reason, conventional stratification becomes problematic because it requires categorizing these continuous factors.

There is a fundamental contradiction between the realities of cluster randomized designs (few sites/clusters from which to sample) and the needs for balance in the resulting design (site pairings that lead to comparable groups of sites). For that reason, we used simulation methods as well described in the literature (Carter 2008; Nietert 2009; Ivers 2012; Moulton 2004;) also as "restricted randomization" or "covariate balanced randomization". This approach seeks to achieve balance for each of the specified characteristics of the clusters (schools).

In each simulation we assigned the 20 schools at random into 2 groups. Then we tested the resulting groups for differences in group means of enrollment, facility score, and attendance. These were the pre-specified school characteristics needed to balance. We then compared these intergroup differences in means to pre-set constraints. In our case we chose a mean difference constraint between schools groups of 10 students for enrollment, 3 for facility percent, and 3 for attendance percent. These constraints we regarded as narrow given the range of the distributions (See Table AX). With these constraints on means alone, however, we found in testing that the distributions could differ in range (and variance). For that reason, for both enrollment and for attendance, we added two more limits on the differences in ranges by school group: 50 for enrollment and 5 for attendance. Altogether, there were 5 constraints.

In testing we found that the yield of balanced treatment allocations across schools was 3 in 1000. For that reason, we proceeded with 2000 simulations to be able to achieve at least one balance allocation of schools. From the resulting set of balanced allocations, we randomly selected one allocation of 20 schools into two groups.

We accomplished this simulation-based randomization with a custom-written program in Stata v 15.1 after finding that published alternatives were too slow and insufficiently flexible for our dual task of achieving balanced means and ranges. The final version of randomization proceeded with a program seed to ensure reproducibility.

	or service services	1 20 5011001	•	
School	Mean	Median	Min	Max
Feature				
Enrollment	463	487	242	644
Attendance (% of students 95%+)	33	30	20	79
Facility Condition Index %	38	39	<1	79

 Table AX1. School Characteristics for balancing. N=20 schools

Wave #2 Second Wave of Public Schools (November 2018)

The second wave of public schools used the same approach as Wave #1. There were 8 public schools in this wave. Using the same program and criteria as in the first wave, we used the same program (modified for only 8 schools) to arrive at 4 schools assigned to intervention and 4 assigned to controls.

Wave #3 Charter School Randomization (February 2019)

Owing to the small number of schools, the lack of data on facility condition, and the need to balance on several factors, we paired the 6 candidate schools and then when the pairs were formed, we randomized one school in each pair to intervention and the other to control.

The primary criterion for pairing was % of days with 95% or greater attendance. That criterion led to the pairing of two of the 6 schools (high attendance). Of the four remaining schools, they were pair on the basis of facility condition and enrollment. Randomization assignment then was by pair. We generated 6 random numbers via a single program from a random uniform generator (using Stata v 15.1) and assigned in order two number to each of the 3 pairs. Once assigned number, each pair then had a school with a higher random number a school with a lower random number. The school with the higher random number became the intervention school in the pair. All decisions about pairing criteria and actual pairing based on those criteria were agreed upon at a meeting on 02/21/2019. Random numbers were generated on 02/22/2019.

3.2 Randomization of children within Schools

Randomization at the child level proceeded using randomly permuted blocks with vary block sizes, as implemented using the Stata program "ralloc" (Ryan 2000). This program used randomly permuted blocks with block sizes of 2 and 4. Randomization was stratified by school and by clinic within school. There were two waves of randomization. The first occurred with the first recruitment of schools and the second with the second wave of schools.

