CHOP Care Network Cobbs Creek, Karabots and South Philadelphia locations each employ a CHW who conduct care coordination and home visits. However, these three CHWs are not able to serve all persistent asthmatics in the practice and do not connect directly with schools to coordinator care for children with asthma. Since our needs assessment revealed caregiver and school nurse concerns regarding asthma management in schools, we focused our pilot on enhancing the connection of CHWs to a local elementary school in order to explore challenges and opportunities for CHWs in elementary school. Thus we piloted the feasibility of a CHW coordinating school asthma care for seven students receiving primary care through CHOP CN Cobbs Creek. After obtaining consent from the parents, the CHW worked directly with the school nurse, principal, and teacher in order to implement elements of the school intervention to improve communication between caregiver, clinical team and school. The CHW enrolled patients at CHOP CN Cobbs Creek and then coordinated with the primary care physician completion of all necessary forms and appropriate

medication/device orders. Despite initial challenges, such as incomplete forms, poor communication between caregiver and nurse, no medications on site, our CHW was able to complete the initial intervention for all 7 children within three weeks of enrollment. Subsequent key informant interviews with the caregivers, school nurse and CHW were overall positive with caregivers and school nurses appreciative of the role of the CHW who coordinated with caregiver and school nurse to make sure that the school had forms, medication and devices needed to provide asthma care for enrolled students. With this success we believe our study design to put CHWs in each of the intervention schools is feasible and the best option for closing gaps and connecting asthma care for school-aged children.

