### 3.1.2 Primary Care Based Intervention

Children who are randomized to the primary care arm will be assigned a primary care community health worker (CHW). We will implement the *Yes We Can*TM Children's Asthma Program  intervention which is a medical-social model based on a chronic care approach, including risk stratification, clinical care management, social care coordination by a community health worker, and primary care asthma champions. This intervention includes asthma education and trigger reduction visits and care coordination. There will be five clinic visits and four home visits over 12 months implemented by the *primary care CHW* who is integrated into the practice.

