### 3.2 Allocation to Treatment Groups and Blinding

The overall design will randomize participating schools to the school intervention (S+) or usual care (S-) based on predefined strata (defined by size, location, public school or public charter school status, etc.) to enhance balance. When children with uncontrolled asthma and their caregivers present in the primary care offices and provide consent to participate, these patients will be randomized either to a primary care CHW (child-level intervention) (P+) or usual care (P-), and this randomization will be stratified by the child's current elementary school and clinic of recruitment to ensure balanced assignment in the factorial design.

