5.1.2 Patient-level analysis – mixed effects models

First, linear mixed effects models with random intercepts and slopes for school, and fixed effects for the school-level intervention, time, and time-by-intervention interaction (the estimate of interest) will be applied. Likewise, the main effect for the child-level intervention and a time*intervention interaction term will be included in the model, and variation across multiple measurements on a child within a school will be accounted for by child-level random effects. This approach then becomes a three-level model with explicitly modeled random effects at the school and child levels.

Synergy of the effect of the two interventions will be estimated by the 3-way interaction between time, the school-level intervention, and the child-level intervention along with all corresponding two-way interactions.

Models will use numerical quadrature with least 12 quadrature points. Models with 16 quadrature points will be used to check sensitivity of results to numerical integration.

This and other individual-patient-level methods can be more efficient (smaller confidence bounds) than cluster (school)-level models. (Hayes and Moulton, section 11.4.2)

We shall exploit mixed effects models to estimate the degree of variation of effects across the 36 schools, both the 18 intervention schools and the 18 control schools by estimating the random slope component of variance and asking whether the observed variation across schools is greater than that expected at random.

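### Clinic is a stratum of the child randomisation but no planned model or test names it; this costs a little precision, and variation between community health workers should be handled as a conditional sensitivity analysis

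*SAP*

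**What the plan says.** The documents agree on the randomisation. Protocol 3.2 states that "this randomization will be stratified by the child's current elementary school and clinic of recruitment". SAP section 2 repeats that "that randomization will be stratified by school and clinic of recruitment", and SAP 3.2 confirms what was done: "Randomization was stratified by school and by clinic within school". SAP 3.4 describes concealment by the same school-by-clinic stratum.

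The analysis sections do not carry clinic forward:

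- **Mixed model (SAP 5.1.2, Protocol 6.4).** The plan is for "linear mixed effects models with random intercepts and slopes for school", plus child effects, giving a "three-level model with explicitly modeled random effects at the school and child levels".
- **GEE (SAP 5.1.3).** Clustering is handled at school level only.
- **Permutation test (SAP 5.1.4).** It is headed as a school-level analysis and does not say how child assignments are to be permuted.
- **Covariates (SAP Table 5.1.2).** Clinic is not listed. It is also absent from the sparse-cell rules (5.2), the subgroup tables (6.1) and the bootstrap (6.1.3), which resamples schools.

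On delivery, Protocol 3.1.2 assigns each child in the primary care arm (P+ in the protocol, A+ in the SAP) a CHW "who is integrated into the practice".

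**The concern.** An analysis normally reflects the factors used to restrict the randomisation. When a stratum is prognostic and the model leaves it out, its variance remains in the residual and the reported standard error is larger than the design earns. The contrasts affected are the primary care ones: A+ v A-, a vs b and c vs d. They serve Specific Aims 1a to 1c.

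Clinic matters in a second way, because it is where the person delivering the A+ intervention works. Children who share a CHW may have correlated responses. The power text (Protocol 6.4, SAP 5.5) describes the primary care contrasts as little affected by clustering, but the clustering it considers is by school. Clustering by CHW would push the standard error in the opposite direction from the omitted stratum, so the two effects have to be kept apart.

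**Working it through.** **Inputs from the documents.** The revised power (SAP section 8) uses 36 schools × 12 children = 432, which is 216 per child-level arm and 108 per cell. The A effect is 0.35 SD with no interaction, residual variance is 1.0 and school variance is 0.0625. Allocation is taken as 1:1 from block sizes 2 and 4. Alpha is 0.05, assumed two-sided. Protocol 9.5 recruits "from up to five primary care centers".

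**Inputs not in the documents (assumed).** The share of variance due to clinic, the number of study CHWs, their caseloads, and the correlation within CHW.

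**1. Reproduce the stated power without any clinic or CHW term.** Power = Φ(δ/SE − 1.96), with SE = √(2/n per arm).

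| Contrast | n per arm | SE | Computed | Stated |
|---|---|---|---|---|
| A+ v A- (432) | 216 | 0.0962 | 0.953 | 0.95 |
| A+ v A- (600) | 300 | 0.0816 | 0.990 | 0.99 |
| c vs d (432) | 108 | 0.1361 | 0.730 | 0.71 |
| a vs b (432) | 108 | 0.1361 | 0.730 | 0.75 |

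The agreement is within what simulation error would explain. The planning variance for these contrasts therefore contains no clinic or CHW component.

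**2. Omitted stratum.** If clinic explains a share R² of the variance of change, the standard error without clinic is too large by 1/√(1 − R²).

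| R² | Ratio | Power at 0.35 SD with clinic in the model |
|---|---|---|
| 0.01 | 1.005 | 0.955 |
| 0.02 | 1.010 | 0.957 |
| 0.05 | 1.026 | 0.962 |
| 0.10 | 1.054 | 0.970 |

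A simulation used 36 schools, 5 clinics, blocks of 2 and 4 within school by clinic, clinic variance 0.05 and 1,500 runs, under two patterns of how schools feed clinics. Mean standard errors without clinic were 0.0982 and 0.0988, against 0.0972 and 0.0974 with it. That is 1.0 to 1.4% larger, so the formula may overstate the gain. Rejection without clinic was 4.5% and 5.5%, compatible with 5%. Strata are thin (432/(36 × 5) = 2.4 children on average), so many blocks stay incomplete and balance on clinic is not exact.

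**3. CHW variation (conditional).** With c CHWs of equal caseload, m = (A+ children)/c, DEFF in A+ = 1 + (m − 1) × ICC, and the ratio of true to reported standard error is √((DEFF + 1)/2). The size of a nominal 5% test is 2 × (1 − Φ(1.96/ratio)).

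| c, ICC | A+ v A-: m, DEFF, ratio, size | a vs b, c vs d: m, DEFF, ratio, size |
|---|---|---|
| 8, 0.01 | 27, 1.26, 1.063, 6.5% | 13.5, 1.125, 1.031, 5.7% |
| 5, 0.02 | 43.2, 1.844, 1.19, 10.0% | 21.6, 1.412, 1.10, 7.4% |
| 5, 0.05 | 43.2, 3.11, 1.434, 17.2% | 21.6, 2.03, 1.231, 11.1% |

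**4. Does school-level adjustment, or a clinic fixed effect, absorb this?** In the same simulation, the A effect was given variance 0.02 across five clinics. The empirical SD of the estimate was 0.116 to 0.118, while the model-based and school-robust standard errors were both about 0.097. Rejection was about 10%, and still about 10% after adding clinic as a fixed effect. Neither device captures the component.

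**5. Why degrees of freedom matter.** With that variance and K = 5, SE = √(2/216 + 0.02/5) = 0.115. Power at 0.35 SD is 0.86 by the normal approximation and 0.78 by t with about 9.4 degrees of freedom.

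**The case against.** A reader might infer that the primary care standard errors are known to be too small and that the A+ v A- test runs at up to 17%. The documents do not support that.

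- They give no number of study CHWs, no caseload and no CHW correlation. The statement that "CHOP Care Network Cobbs Creek, Karabots and South Philadelphia locations each employ a CHW" (Protocol 1.1) is background on existing staff, not a description of study staffing. The upper figures need five CHWs and a correlation of 0.05 together.
- The inflation arises only if the effect differs between CHWs. If the intervention does nothing for any child, this component is absent.
- It also requires inference to a wider population of CHWs. The SAP's remarks on generalizability (5.1.4) concern variation across schools, so the target for CHWs is left open. If inference is conditional on the participating CHWs, the extra variance does not apply.
- The power text speaks only of clustering within schools, and SAP 5.5 labels it historical. It makes no claim about CHWs.

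All of this stands, and it is why the CHW issue is put as a condition. It can also be said that clinic might enter through the weights for unbalanced covariates (SAP 5.1.2) or through covariates linked to dropout (SAP 5.3). Either route is possible, but neither names clinic, and neither would model variation between CHWs. The omission of the stratum is not answered.

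**Conclusion.** Clinic is a randomisation stratum and is missing from every named model and test; confidence in this is high. The consequence that follows is minor and conservative: a standard error about 0.5 to 5% too wide for an assumed clinic share of 1 to 10%, with power for A+ v A- moving from 0.953 to at most about 0.97. It creates no false-positive risk. Correcting it is a free improvement.

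CHW variation is a separate matter, and confidence in its size is low. If the effect varies between CHWs and inference is meant to reach beyond them, the true standard error exceeds the reported one by about 6 to 43% for A+ v A- at n = 432, and by about 3 to 23% for a vs b and c vs d, given 5 to 8 CHWs and a correlation of 0.01 to 0.05. The larger range must not be applied to the cell contrasts, which have 108 children per cell. What the plan lacks here is a stated target of inference and a check; an error in the standard error has not been shown.

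**What to change.** 1. Add clinic of recruitment as a fixed effect in the mixed and GEE models (SAP 5.1.2 and 5.1.3). Because the contrasts are differences in change over time, include a clinic-by-time term as well.
2. State in SAP 5.1.4 that child assignments are permuted within the school-by-clinic strata used for randomisation.
3. Pre-specify a sensitivity analysis with a random effect for primary care CHW that applies to A+ children only, use small-sample degrees of freedom, and report the variance. If CHW identity is not recorded, use clinic in its place. Alternatively, state that inference on the primary care effect is conditional on the participating clinics and CHWs. Item 1 does not replace this step.

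**Cost.** SAP wording, and four or five parameters per clinic term for five or six clinics. Clinic is already held as a stratum in REDCap (SAP 3.4). Whether CHW identity is in the analysis data is not stated and should be confirmed. With so few CHWs the variance will be imprecise, which is why item 3 is a sensitivity analysis. The SAP was finalised in September 2022, so this needs a dated amendment before outcomes are analysed; otherwise SAP 9.1 makes the added analyses exploratory.
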